Participants will undergo two visits at OHSU that will evaluate missed meal bolus detection. Participants will arrive at approximately 7am for all visits, be monitored through the afternoon and discharged before dinner. See **Figure 1** for a diagram of the study flow. During each of these intervention visits, participants will wear an Omnipod to deliver insulin and a Dexcom G6 CGM to measure glucose. The closed loop system will receive activity data through a Polar M600 watch worn by the participant. The studies will test the ability of the system to adapt to a missed meal bolus. For one missed meal bolus study, glucose will be controlled using the Robust R-AP closed-loop mode. During the other missed meal bolus study, glucose will be controlled using the MPC closed-loop mode. For the R-AP study, participants will eat self selected meals at 10 am and 2pm. The 10am meal will be the only meal given during the MPC study. The 10am meal will be the same across both arms. A meal bolus will not be given before any meals.

Figure 1: Study Flow Design

Subject Criteria

Inclusion Criteria:

- 1. Diagnosis of type 1 diabetes mellitus for at least 1 year.
- 2. Male or female participants 18 to 65 years of age.
- 3. Current use of an insulin pump for at least 3 months with stable insulin pump settings for >2 weeks.

- 4. HbA1c $\leq 10.5\%$ at screening.
- 5. Total daily insulin requirement is less than 139 units/day.
- 6. Willingness to follow all study procedures, including attending all clinic visits.
- 7. Willingness to sign informed consent and HIPAA documents.

Exclusion Criteria:

- 1. Individual of childbearing potential who is pregnant or intending to become pregnant or breast-feeding, or is not using adequate contraceptive methods. Acceptable contraception includes birth control pill / patch / vaginal ring, Depo-Provera, Norplant, an IUD, the double barrier method (the woman uses a diaphragm and spermicide and the man uses a condom), or abstinence.
- 2. Any cardiovascular disease, defined as a clinically significant EKG abnormality at the time of screening or any history of: stroke, heart failure, myocardial infarction, angina pectoris, or coronary arterial bypass graft or angioplasty. Diagnosis of 2nd or 3rd degree heart block or any non-physiological arrhythmia judged by the investigator to be exclusionary.
- 3. Renal insufficiency (GFR < 60 ml/min, using the MDRD equation as reported by the OHSU laboratory).

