After a run-in period of 2 hours whereby the participants are using the AP algorithms, participants will eat self selected meals around 10 am. During the R-AP study only, another meal will be given four hours later around 2 pm. The self selected meals will have a minimum of 45 g of carbohydrates, and a maximum of 120 g of carbohydrates. These self selected breakfasts will be identical across both study sessions. Participants will not enter a meal bolus for the meals. CBG and blood ketone measurements will be taken every 30 min (for safety purposes only, not for input into the AP systems) until study discharge. If CBG >250mg/dL before the lunch meal, then study will be stopped early and the participant will be given the option to return on a different day for the second meal.

The study will be stopped if:

- (1) the CBG reaches > 300 mg/dL with ketones > 0.5 mM,
- (2) the CBG reaches > 300 mg/dL for over an hour (even when ketones are <0.5 mM),
- (3) the CBG reaches > 450 mg/dL,
- (4) participants exhibit nausea or vomiting or both.

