Participants can be discharged after 4pm when: (1) CBG >80 and < 250 mg/dl, (2) ketones \leq 0.2 mM and (3) the participant is feeling well. For values outside this range, treatment will be at the discretion of the study investigator. Participants will be given a snack to take with them for the trip home. Participants will also be advised to monitor their glucose for any symptoms of hyperglycemia or hypoglycemia, before their next meal, and at bedtime.

Discharge from clinic

The study will be terminated and the participant's own insulin pump will be restarted. The study investigator will consult with the participant regarding appropriate insulin dosing for the remainder of the day. The Polar watch, Omnipods and Dexcom sensor will be removed from the participant. All infusion sites and the sensor site will be inspected for signs of irritation or infection. In addition, the sensor will be inspected for the possibility of breakage or fracture. If there is any evidence of sensor breakage, it will be recorded. If an area of inflammation of 1 cm or greater exists around the point of insertion, a de-identified photograph will be taken of the area and the participant will return 1-3 days later for a follow-up visit.

If a study visit is stopped prematurely, such as due to technical problems, the participant will be asked if they can repeat the study visit that was terminated early with additional compensation provided. Repeating the study visit will be optional.

Hypoglycemia Treatment Guidelines

• CBG < 70 mg/dl

Give 15 grams of oral carbohydrate.

Repeat treatment every 15 minutes as needed to raise blood glucose ≥70 mg/dl.

• Presence of STUPOR, LOSS OF CONSCIOUSNESS, or SEIZURE

Give 1 mg glucagon IM

Verify that insulin is turned off.

Further management per study investigator.

Cleaning and Disinfecting

All devices will be cleaned and disinfected between participants. The smart phone, Dexcom G6 transmitter and Omnipod PDMs are cleaned by study staff. Technicians who are disinfecting units will wash hands thoroughly and wear gloves. All items will undergo intermediate-level disinfection using Oxivir TB disposable wipes. The disinfectant will be applied and allowed to air dry. After disinfection, when the units are completely dry, they will be placed in a sealed bag labeled with participant information.

Stopping Rules

Individual study stopping rules

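### The discharge rule rests on one fingerstick value and ignores glucose trend, insulin on board and time since the last bolus, which matters most after the 2 pm meal on the R-AP visit

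*Combined protocol and SAP*

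**What the plan says.** Under 1 day Treatment Visits, the rule for leaving is "Participants can be discharged after 4pm when: (1) CBG >80 and < 250 mg/dl", with ketones no higher than 0.2 mM and the participant feeling well. The next sentence adds: "For values outside this range, treatment will be at the discretion of the study investigator". The Protocol Summary says participants will "be monitored through the afternoon and discharged before dinner".

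The same rule serves both visits, but the meals differ. For the comparator visit the Protocol Summary states: "The 10am meal will be the only meal given during the MPC study". For the other visit: "During the R-AP study only, another meal will be given four hours later around 2 pm". Meals contain 45 to 120 g of carbohydrate, and the participant enters no bolus for them.

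Insulin can nonetheless be given late, by two routes described in the same section:

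- **R-AP detection bolus.** If R-AP detects the meal, it doses from its own carbohydrate estimate, which the user can change. An investigator first reviews the dose for insulin on board and time since the meal.
- **Investigator bolus.** If one of the first three glucose or ketone stopping criteria is reached, the investigator calculates a meal-plus-correction bolus, also weighing CGM trend. Further doses may follow about every three hours. This route is not restricted to one system.

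Until discharge, "CBG and blood ketone measurements will be taken every 30 min", and CGM arrives every five minutes. At discharge, "The Polar watch, Omnipods and Dexcom sensor will be removed from the participant", the participant's own pump restarts, and the investigator advises on insulin dosing for the rest of the day. In addition, "Participants will be given a snack to take with them for the trip home", with advice on self-monitoring.

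**The concern.** The protocol treats insulin on board, time since the meal and (for the investigator bolus) CGM trend as relevant when a dose is set. It does not carry them into the decision to let the participant go. A CBG of 85 or 100 mg/dl means one thing when glucose is flat and another when it is falling with a bolus still acting. The rule cannot tell these apart.

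The feature that R-AP adds is a bolus delivered after eating has begun and sized from an estimated carbohydrate content. A dose too large for the meal would show itself some time later, possibly after the participant has left. At that point staff presence, the 30-minute CBGs and the study CGM have ended, and the participant may be travelling home. What is at stake is avoidable hypoglycemia outside the clinic.

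**Working it through.** The plan gives no figure of its own for this interval, so the check is clock arithmetic plus a simple projection.

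**1. Time from last meal to earliest discharge** (meal times from the Protocol Summary and 1 day Treatment Visits)
- R-AP visit: 4:00 pm − 2:00 pm = 2 h.
- MPC visit: 4:00 pm − 10:00 am = 6 h.

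Meal times are approximate, so a late second meal shortens the first interval.

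**2. Age of a detection bolus at 4 pm** (Appendix C, missed-meal alert: carbohydrate presumed eaten about 25 min before the alert; alert expires after 20 min)
- Alert: 2:00 pm + 25 min = 2:25 pm.
- Acknowledged after 0 to 20 min: 2:25 to 2:45 pm.
- Age at 4:00 pm: 95 to 75 min, less any time taken by the investigator's review.

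Staff respond to all alerts, so the figure is likely nearer 95 min. The 25 minutes is what the algorithm presumes, not a documented detection time. Slower detection would make the bolus more recent.

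**3. Share of that bolus still active** (illustration only; the documents give neither an action time nor a decay curve)

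Assume linear decay: share = 1 − age/duration.
- Duration 3 h: 1 − 95/180 = 47%, to 1 − 75/180 = 58%.
- Duration 5 h: 1 − 95/300 = 68%, to 1 − 75/300 = 75%.

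**4. Investigator-given bolus, either visit**

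No minimum interval from dose to discharge is set, so its age at 4 pm cannot be bounded from the text. The triggering CBG is above 300 mg/dl and discharge needs a value below 250 mg/dl. Some time must therefore pass, but the rule does not say how much.

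**5. Who passes the glucose criterion while heading low**

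Fall rate that brings glucose G to 70 mg/dl in 30 min = (G − 70)/30:
- G = 85: 15/30 = 0.5 mg/dl/min.
- G = 100: 30/30 = 1.0 mg/dl/min.

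Both values lie between 80 and 250 mg/dl, so with acceptable ketones and no complaints both participants may leave.

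**6. Choice of threshold for a fix**

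The protocol has a prediction rule for a lost sensor: insulin is suspended if the last value was 70 to 140 mg/dl and is predicted below 90 mg/dl within 30 min. Applied to discharge, the fall rate needed is (G − 90)/30. At G = 85 this is −5/30 = −0.17 mg/dl/min, so someone flat, or even rising slowly, is still predicted below 90. Stable participants at 81 to 89 mg/dl would be held. A projection to 70 mg/dl avoids this, because a flat 85 projects to 85.

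**7. Data already in hand at 4 pm**

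From 2 to 4 pm: 120/30 = about 4 CBGs and 120/5 = 24 CGM readings.

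**The case against.** The case on the other side is substantial. The rule permits discharge and does not compel it; 4 pm is a floor. The investigator is already involved at discharge, advising every participant on insulin for the rest of the day, and would naturally think about a recent dose. The detection bolus has been reviewed for insulin on board, and the dosing formula subtracts it. Staff are present throughout, CBG is checked every 30 minutes, and the floor is above 80 mg/dl. Participants are established pump users without hypoglycemia unawareness or recent severe hypoglycemia, and they leave with a snack and advice. Carbohydrate from a 45 to 120 g meal may still be absorbing two hours later and offset a fall. The worrying state needs several things to coincide, and if the second meal is undetected or not given that day, the detection bolus does not exist.

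All of this stands as a reason to keep the priority modest. It does not remove the point, because none of these safeguards makes leaving depend on trend or active insulin. The dosing consultation concerns later doses and is not a condition of discharge.

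Two stronger readings are tempting:

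- **A fault of the R-AP visit alone, measured by 2 h against 6 h.** That contrast measures time since eating, whereas the hazard is recent insulin. The investigator-given bolus can occur on either visit, so a fix limited to R-AP would miss it.
- **A contradiction with the lost-sensor rule, because the protocol would suspend insulin in a state where it allows discharge.** That rule governs automated basal delivery without a sensor, and its action is suspension of insulin. It also captures stable participants, so it does not show that everyone it flags is unsafe to leave.

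**Conclusion.** The point holds as a gap in a stated safety rule: a participant at 85 to 100 mg/dl, falling, with recent bolus insulin, can meet every written condition for discharge. On the R-AP visit the detection bolus is nominally 75 to 95 minutes old at the earliest discharge time. This assumes a 2 pm meal, the presumed 25-minute lag and dosing at acknowledgement. The share still active, 47% to 75%, rests wholly on the assumed linear decay and 3 to 5 h action time. The projections also assume that CBG and CGM agree and that the fall continues at a constant rate.

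The documents do not show how often this would happen, so they do not support a claim that participants will be sent home into hypoglycemia. Nor should a reader infer damage to the trial's answer. The primary endpoints and the secondary objective use the four hours after the first meal, about 10 am to 2 pm, which end before discharge. The secondary endpoint list refers to meals in the plural, but the MPC visit has only one, so the comparison between systems rests on the first meal.

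This is a cheap participant-safety improvement, of low-to-moderate priority.

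**What to change.** Add to the discharge rule, for both visits:

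> Before discharge the investigator reviews the time since the last meal or correction bolus, the remaining insulin-on-board and the CGM/CBG trend. A participant with recent bolus insulin whose glucose is falling and projected to go below 70 mg/dl within 30 minutes (or another threshold the investigators set) stays under observation, with CBG rechecked every 30 minutes, until this no longer applies.

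The 90 mg/dl lost-sensor threshold should not be borrowed, for the reason in step 6. The investigators should also state what counts as recent and over what window the trend is read.

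The cost is one amendment to the text and one line on the discharge checklist, using data already collected and no new device. Some participants will leave somewhat later, which may strain the intention to discharge before dinner, and a short-window projection will hold a few who would not have gone low.

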An assessment will take place at the beginning of the participant's first closed-loop study. We will inquire whether the participant has had changes in their medications and/or medical history to confirm the participant hasn't developed any study exclusion criteria. A capillary blood glucose (CBG) will be obtained and measured by a Contour Next glucose meter. When they arrive, participants will be given 15-20 grams of oral carbohydrate if the CBG reading is less than 70 mg/dl. CBG values > 300 mg/dl will be managed at the discretion of the investigator with a correction bolus and serum ketones will be checked. If serum ketones are ≥ 0.6 mM, the study will not be started and insulin therapy will be guided by the onsite investigator.

During each visit, glucose will be controlled using either: 1) the OHSU Robust R-AP closed-loop mode or 2) the OHSU MPC closed-loop mode. The order of the visits will be randomized. A code team is available by page at all times in all locations.

An Omnipod will be filled with Novolog or Humalog insulin for all studies. The Omnipod will be primed and inserted into the skin of the participant's abdomen or flank as directed by the manufacturer. Participants will disconnect his/her own pump and remove his/her own insulin infusion set once insulin delivery has started via the Omnipod. Participants will wear a Polar watch to inform the controller. The research staff will initialize the system and begin the closed-loop study. Two staff will review each of the settings to confirm the settings are inputted correctly. A member of the study staff will remain with the participant for the duration of the study with the study investigator on call. Research staff will set up and run the system and respond to all alerts.

The algorithm will push data up to a cloud server that can be monitored remotely every 5 minutes. The iPancreas will generate alerts on the smartphone according to Appendix D. In order to push alerts to study coordinators and study investigators, the cloud server used for remote monitoring will have a drop down menu for study staff to sign in and out for the duration of their monitoring shift. Each study coordinator and investigator listed in the menu will have a cell phone number on file that can receive texts with pushed alerts.

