The R-AP is a modified MPC algorithm. A new feature in the algorithm includes a model for missed meal insulin detection. The model includes estimations for carbohydrate consumption based glucose patterns to determine if that person has consumed a meal without announcing it to the system. We refer to this algorithm as Missed Meal Insulin Detection. Our Missed Meal Insulin Detection algorithm is unique in that it presumes that the patient will generally announce their meals to the system. However, if the participant does not announce, the algorithm will detect it using machine learning methods, and then adjust dosing based on this detected meal.

Statistical methods

The primary study endpoints are (1) incremental area under the curve (AUC) of glucose in the 4 hours following unannounced meals and (2) percent of time with glucose sensor 70-180 mg/dL. The hypothesis to be tested is the R-AP closed-loop system will increase time in range and decrease AUC as compared to the MPC-AP closed-loop system. We will estimate the difference between systems using a fixed effect in a standard 2x2 crossover model with a random participant effect. While we do not anticipate statistically significant effects for the following, we will also control for sequence (AB or BA) and period (1 or 2).

We anticipate that the primary outcomes will be approximately normally distributed. We will review the appropriateness of this assumption using both goodness-of-fit tests and diagnostic plots, such as quantile-normal plots. If the normality assumption holds, possibly with a transformation of the outcome, we will test the difference between the robust-AP and standard MCP visits using a paired t-test. In the case of mild departures from normality or unequal variances at the two time points, we will re-analyze the primary outcome as the difference between the two visits using bootstrapped standard errors, which avoid distributional assumptions. We will use two-sided tests at the 0.05 level of significance.

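### The system effect is estimated with period adjustment but tested by a paired t-test without it, and unequal visit variances wrongly trigger an under-specified bootstrap that can exceed 5% at n = 15

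*Combined protocol and SAP*

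**What the plan says.** All the rules at issue are in the Statistical methods section.

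- **Estimation:** "We will estimate the difference between systems using a fixed effect in a standard 2x2 crossover model with a random participant effect". Sequence and period are also to be controlled for, although the authors expect little from them: "While we do not anticipate statistically significant effects for the following".
- **Test:** if normality holds, possibly after a transformation, "we will test the difference between the robust-AP and standard MCP visits using a paired t-test" (MCP is evidently a slip for MPC).
- **Fallback:** "In the case of mild departures from normality or unequal variances at the two time points", the plan continues, "we will re-analyze the primary outcome as the difference between the two visits using bootstrapped standard errors, which avoid distributional assumptions".
- **Level:** "We will use two-sided tests at the 0.05 level of significance".

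Under 1 day Treatment Visits, "The order of the visits will be randomized"; no method of balancing the sequences is given. Study Population sets the sample at fifteen. Power Analysis justifies that number by feasibility and says the outcome estimates and their variability will inform a larger trial. The plan does not say which analysis supplies the decisive p-value, what counts as unequal variances, or what reference distribution goes with the bootstrapped standard error.

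**The concern.** There are three linked faults.

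1. **Estimate and test differ.** The model removes a period effect and the paired t-test does not. Fifteen participants cannot be split evenly, so a period effect enters the paired test twice: it shifts the mean difference and it inflates the SD of the differences. The p-value can then disagree with the estimate printed beside it.
2. **The variance trigger is wrong.** A paired test uses only the within-person differences. Unequal variances at the two visits violate none of its assumptions, nor those of the model's treatment term when pairs are complete. Two algorithms may well differ in variability, so this trigger could move valid data off a 5% test.
3. **The fallback is misdescribed.** A bootstrapped standard error is only a standard error. Turning it into a p-value needs a reference distribution, so it does not by itself remove distributional assumptions. Uncorrected, it is too small at n = 15.

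The larger trial is to be planned from these estimates and their variability. An SD inflated by an unremoved period effect would mislead that planning.

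**Working it through.** **Inputs.** From the documents: n = 15 pairs, two-sided alpha 0.05, randomised visit order. Assumed, because the documents give none: period effects of 0 to 1 SD of the paired difference, sequence splits of 8/7, 9/6 and 10/5, and a treatment effect of 0.75 SD for power.

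**The plan's own figure.** The paired t-test on 14 df has critical value 2.145, and P(|t14| > 2.145) = 0.050. With normal differences and no period effect it holds the stated level.

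**Period effect.** Write each difference as d = tau + pi·s + e, where s = +1 or -1 by sequence, pi is the period effect and e has SD 1. The paired mean has bias pi·(n1 - n2)/15, which is pi/15 at 8/7, pi/5 at 9/6 and pi/3 at 10/5. The expected variance of the differences is 1 + pi²·[15 - (n1 - n2)²/15]/14. At 8/7 this is 1.27 for pi = 0.5 and 2.07 for pi = 1. The model estimate is the mean of the two sequence means, tested with pooled variance on 13 df; it is unbiased. Simulated level of the paired test (400,000 trials per cell):

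| Split | pi = 0 | 0.25 | 0.5 | 1 |
|---|---|---|---|---|
| 8/7 | 5.0% | 4.4% | 3.1% | 0.8% |
| 9/6 | 5.0% | 4.7% | 4.1% | 2.2% |
| 10/5 | 5.0% | 5.4% | 6.2% | 6.8% |

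The model's treatment term stays at 4.9-5.0%. Averaged over simple randomisation the paired test is at 5.0-5.1%, so the problem concerns the split actually obtained.

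For a 0.75 SD treatment effect at 8/7 the model has 76% power. Two figures in a cell are for the two directions of the period effect; disagreement means that one test is significant at 0.05 and the other is not.

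| Period effect | Paired-test power | Tests disagree |
|---|---|---|
| 0 | 77% | 2.9% |
| 0.5 SD | 73% or 64% | 5.3% or 12.5% |
| 1 SD | 54% or 36% | 22% or 40% |

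**Unequal visit variances.** With visit SD ratios of 1, 2 and 4 and correlations of 0 and 0.5 (200,000 trials each), the paired test's level was 4.9-5.1%.

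**Bootstrapped SE.** For a mean difference, the uncorrected bootstrapped SE is the ordinary SE times sqrt(14/15) = 0.966; a direct bootstrap with 200,000 resamples also gave 0.966. The fallback statistic is therefore 1.035 times the ordinary t. It rejects when the ordinary |t| exceeds 2.145 × 0.966 = 2.07 (t14 reference) or 1.96 × 0.966 = 1.89 (normal reference). For normal data the exact level is P(|t14| > 2.07) = 5.72% or P(|t14| > 1.89) = 7.91%. With 13 pairs these become 5.8% and 8.4%.

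| Differences | Paired t | Bootstrap SE, t14 | Bootstrap SE, 1.96 |
|---|---|---|---|
| Normal | 5.0% | 5.7% | 7.9% |
| Skewness 1 (gamma) | 6.0% | 6.7% | 8.9% |
| t3 tails | 4.2% | 4.9% | 7.1% |
| Normal, 8/7, 1 SD period effect | 0.8% | 1.0% | 1.7% |

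On any given data set the uncorrected fallback is never stricter than the paired test.

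**Two-step rule.** The plan names no variance test, so assume a Pitman-Morgan test at 0.05, normal data and visit correlation 0.3-0.7. It fires in 33-51% of trials at a visit SD ratio of 1.5 and in 74-91% at a ratio of 2. Overall size with 1.96 is then 5.8-6.4% and 6.9-7.5%; with t14 it is at most 5.6%. With only a Shapiro-Wilk trigger at 0.05 it is 5.1-5.2%. The plan's optional transformation was not simulated.

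**The case against.** The best reply is that most of the damage depends on things the plan does not state. The authors expect no period effect. Visits are same-time single clinic days with an identical 10 am meal and a 3 to 30 day washout. Without a period effect the paired test is exact and slightly more powerful than the model. At 8/7 or 9/6 its level is at or below 5%, and simple randomisation gives one of those splits about 70% of the time: 2 × (6435 + 5005)/32768 = 69.8%. Inflation needs 10/5 or worse together with a real period effect.

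The 7-9% figures for the fallback need the 1.96 cut-off; an SE corrected for sample size with a t14 reference is exactly the paired t-test. Re-analysing could also mean a supporting analysis beside the first. And this is a feasibility study.

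These limits stand, and they keep the stakes modest. They do not remove the faults. The plan commits to period adjustment and then omits it from the test, so expecting no effect is no reason for the mismatch. Substitution is the natural reading of the fallback sentence, and on either reading the decisive p-value is not identified. The variance trigger is wrong for complete pairs whatever the period effect. If pairs are incomplete, a random-participant model's weighting does use a common variance, but a paired test uses complete pairs only.

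**Conclusion.** The concern holds. Estimate and test come from different analyses, the unequal-variance trigger has no basis for paired differences, and the claim made for the bootstrapped standard error is incorrect. These follow from the plan's text alone.

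Their size depends on assumptions. If the period effect is nil, the paired test holds 5% and usually agrees with the model. At 0.5 to 1 SD it becomes conservative and loses power at 8/7, and is liberal at 10/5 (6.2-6.8%), with a bias of one third of the period effect. The fallback can exceed 5% at n = 15: by 0.7 points on normal data with an uncorrected SE and t14, or by 2.9 points with 1.96. It does not do so if the SE is corrected and t14 is used. The plan should be changed, but the fault does not threaten a feasibility study as a whole.

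**What to change.** - For each primary endpoint, take the estimate, its confidence interval if reported, and the p-value from the treatment term of the crossover model already specified, with a t reference (13 df with 15 completers). Drop the separate paired t-test.
- Delete unequal variances at the two visits as a trigger.
- If a bootstrap is kept for non-normality, apply it to the period-adjusted contrast: resample the pooled model residuals, multiply the SE by sqrt(15/13), and refer the statistic to t13. This reproduces the model test (5.0% for normal data), so it is safe but does not cure skewness; dropping the bootstrap would lose little. Correcting within each sequence instead gives 5.1% at 8/7 but 6.0% at 10/5.
- Remove the clause saying that bootstrapped standard errors avoid distributional assumptions.
- Optionally, add a re-randomisation test of the sequence labels as a sensitivity analysis.

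The cost is wording, plus some power when there is no period effect. For an assumed 0.75 SD treatment effect, power falls from 77.1% to 76.4% at 8/7, 74.9% at 9/6 and 71.7% at 10/5. The lost degree of freedom accounts for 0.5 points. The rest comes from unequal sequence sizes, which multiply the variance of the contrast by (15/4)(1/n1 + 1/n2) = 1.004, 1.042 and 1.125.
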